## 7.2.2 Secondary Endpoints

Consistent with the secondary study objective, the following endpoints will be assessed on Day 35 and Day 49 across all 4 dosing arms:

- Concentrations of TFV, FTC, TFV-DP and FTC-TP in blood
- Concentrations of TFV and FTC in vaginal and rectal secretions
- Concentrations of TFV and FTC in vaginal and rectal tissue homogenates
- Concentrations of TFV-DP and FTC-TP in unselected and CD4+ vaginal and rectal tissue cells and tissue homogenates
- Concentrations of TFV, FTC, TFV-DP and FTC-TP in fluid (rectal, vaginal, semen), cells, and tissue homogenate.
- Adverse experiences, including safety laboratory studies (hematological, renal, hepatic function)

## 7.3 Accrual, Follow-up, Retention, and Sample Size

A total of 32 evaluable men and women will be enrolled over a period of approximately 6 months at multiple sites. An equal number of participants (8 per arm) will be randomized into each of the four dosing arms. Each enrolled participant will be followed for 7 weeks.

Research participants may miss one of the following pre-steady-state study visits when on drug (Day 7, Day 14, Day 21) and remain in the study and remain eligible for evaluation in the PK outcome analysis of the study. Day 0, Day 28, Day 35, and Day 49 are required for a participant to be considered evaluable. Optimally, all study product dosing will occur on the date prescribed. However, some forgiveness of strict adherence to the schedule will be tolerated as long as the total dose within each week is consistent with the prescribed total. Therefore, for arms 1, 2, and 3, study drug dosing can be delayed by 2 days, during the first 3 weeks of the study. Thereafter, all doses in week 4 and 5 must be taken as scheduled. In Arm 4, all doses for research participants must be taken as scheduled. Failure to comply with these scheduled requirements will result in discontinuation from the study after a final safety evaluation.

Evaluable participants are expected to represent 95% of participants enrolled into the study. No adjustments are made for retention losses since all discontinued or inevaluable participants will be replaced. Each study site will establish participant retention procedures to target lost-to-follow-up rates of <5% in order to minimize additional enrollments to compensate for inevaluable participants.

For the intensive cohort, a subject must have all blood on Days 0, 28, 35 and 49, and vaginal, seminal, and rectal samples on Days 35, and 49 to be evaluable. If the subject is inevaluable for

the intensive cohort, but has met evaluability criteria for the non-intensive cohort AND there is an opening in the non-intensive arm-gender cohort matching the subject, then they may be switched in assignment to the non-intensive cohort. If the intensive subject fails to complete all required samples OR there is not an opening consistent with their gender/arm, then the participant is discontinued after the final safety evaluation. In either case, the subject needs to be replaced in the intensive sampling group.

Typical sample sizes for phase I PK studies generally range between 6 and 12 subjects per arm. A number of different approaches have been used to assess dose proportionality in the literature (Gough et al., 1995; Hummel et al., 2009; Smith et al., 2000). We consider the sample size using the following two approaches:

1) fitting a simple linear regression model between the PK parameter (y) and dose

$y = \alpha + \beta \text{dose}$ , where the hypothesis that  $\alpha = 0$  is tested and the lack of fit of the model is generally tested by adding a quadratic term; and

2) using the power model approach to fit  $\log(y) = \alpha + \beta \log(\text{dose})$ , where 90% CI around  $\beta$  is

compared to the limits  $(1 + \frac{\ln(\theta_L)}{\ln(r)}, 1 + \frac{\ln(\theta_U)}{\ln(r)})$ , where  $(\theta_L, \theta_U)$  are the pre-defined limits and  $r$

is the ratio of the highest to the lowest dose. The power model and the CI approach has become more preferred choice in recent years (Gough et al., 1995; Smith et al., 2000), however, Hummel et al. (Hummel et al., 2009) suggested that the choice of bioequivalence default values of  $\theta_L = 0.8$  and  $\theta_U = 1.25$  seems to be impractically strict when applied over a dose range that is more than doubling apart and proposed a more lenient criterion  $\theta_L = 0.5$  and  $\theta_U = 2$ .

The empirical power of both approaches are computed using a simulation study with the following steps:

1. Generate random samples of size n from a normal distribution

$N(\mu = 14 \times \text{dose}, sd = CV \times \mu)$ , where 14 is the weekly dosing Day 35  $C_r$  from Figure 1-1, and dose = 1, 2, 4 and 7 for Arm 1 to 4 respectively.

2. Fit linear regression model  $y = \beta_0 + \beta_1 \times \text{dose} + \beta_2 \times \text{dose}^2$  (Smith et al., 2000) and test for nonsignificant intercept and quadratic terms (Zhou et al., 2006).

3. Fit linear model  $\log(y) = \alpha + \beta \log(\text{dose})$  and compare 90% CI of  $\beta$  with the pre-specified critical interval  $(1 + \frac{\ln(0.5)}{\ln(7)} = 0.64, 1 + \frac{\ln(2)}{\ln(7)} = 1.36)$

4. Repeat steps 1-3 for 1000 times. The empirical power is calculated as the proportion of the replications in which nonsignificant intercept and quadratic term holds for approach 1 or the CI falls entirely within the critical interval for approach 2.

There are at least 4 available groups of participants for estimating inter-individual variability to be used here for the purposes of estimating sample size. These studies, however, present a broad range of CV. In one HIV prevention study in which research participants took a daily oral dose of TDF, the inter-individual coefficient of variation in TFV-DP concentrations in PBMCs was 46%. Hawkins et al. (Hawkins et al., 2005) report range of median concentrations of 85-110 fmol/M cells (Table 7-1) for 7 subjects evaluated. Imputing values from the extremes of this range would yield a CV of approximately 14%. Pruvost et al. (Pruvost et al., 2009) report (Table 7-3) range of TFV-DP CV% as 28, 36, 35, 54 in a drug interaction study with LPV/r and NVP. Pruvost et al. (Pruvost et al., 2005) report (Table 7-1 groups 1 and 3) inter-individual CV% of 42% (group 1) and 83% (group 3). Note none of the above studies were done in healthy volunteers with one single drug dosed under direct observation. Given that the DOT used in this study is likely to reduce the variability, a CV estimate of 25-35% seems to be realistic. In the simulation study, we explored a range of CV values from 25% to 45%.

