**Table 7-1. Power for dose proportionality assessment,  $\alpha = 0.05$**

Sample size (per arm)	CV	Simple linear model and hypothesis testing approach	Power model and CI approach
N=6	25%	93.3%	98.4%
	35%	93.6%	74.9%
	45%	93.2%	33.3%
N=8	25%	95.0%	99.7%
	35%	95.1%	81.1%
	45%	93.8%	41.8%
N=10	25%	95.5%	99.8%
	35%	95.0%	85.0%
	45%	94.4%	43.5%
N=12	25%	96.1%	99.7%
	35%	93.9%	85.2%
	45%	94.6%	43.6%

Simulation results suggested that either 6 or 12 participants per arm would yield sufficient power for a range of coefficient of variation parameters (25% - 45%) when dose proportionality is assessed using hypothesis testing approach based on simple linear regression model. However, the empirical power associated with the power model and the CI approach is more heavily depend on the value of CV in the relevant range. With  $CV \leq 35\%$ , a reasonable degree of variation given the argument above, we would have  $\geq 81\%$  power to claim dose proportionality with 8 participants per arm. For this reason, in addition to cost and operational considerations, 8 subjects per arm was selected as the minimum size to provide adequate power for the dose-proportionality assessment, our primary objective.

For the secondary objective assessing difference in intracellular TFV-DP and FTC-TP steady state Day 35  $C_\tau$  (pre-dose concentration) between men and women, we assume the mean TFV-DP steady state concentration  $C_\tau$  is 100 fmol/ $10^6$  cells, and the coefficient of variation between people is 35%. Based on the results from Van Belle and Martin (Van Belle and Martin, 1993), we would have only 35% power to detect a 1.5 fold difference (i.e., 100 to 150) between men and women within each dosing arm if an arm has 4 men and 4 women (i.e., a total of 32 participants distributed evenly into four arms, 50% men and 50% women). If dose-proportionality holds, then we would be able to make the comparison between men and women across dosing arms. We then would have 89% power to detect a 1.5 fold difference with a total sample size of 32 (16 men and 16 women) selected for this study. Table 7-2 provides power for a range of CV, sample size and minimal detectable difference. The power would reduce with smaller sample size, smaller minimal detectable difference, and larger CV.

**Table 7-2. Power to detect the minimal detectable difference (in fold) for various sample sizes and coefficients of variance (CV)**

CV	N per group	Minimal detectable X-fold difference		

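### Table 7-1 takes logs of untruncated normal draws, which distorts its power-model cells at CV 35% and 45%, and its linear column is about 1 − alpha rather than power

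*Protocol*

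**What the plan says.** Protocol 7.3 gets its power from a four-step simulation.

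- Step 1: "Generate random samples of size n from a normal distribution" with mean 14 × dose and SD equal to CV × mean, "and dose = 1, 2, 4 and 7 for Arm 1 to 4 respectively".
- Step 2 fits a quadratic regression of y on dose. Step 3 fits log(y) on log(dose) and compares the 90% CI of the slope with 0.64 to 1.36.
- Step 4 repeats this 1000 times. Power is the share of replicates "in which nonsignificant intercept and quadratic term holds for approach 1", or in which the CI lies inside the interval for approach 2.

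On variability, 7.3 cites a study in which the "coefficient of variation in TFV-DP concentrations in PBMCs was 46" per cent, among other sources, and then argues that "a CV estimate of 25-35% seems to be realistic". Table 7-1 covers CVs of 25, 35 and 45%.

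The text after the table says of the linear approach that "either 6 or 12 participants per arm would yield sufficient power". For the power model with CV up to 35% it claims at least 81% "power to claim dose proportionality with 8 participants per arm", and concludes that "8 subjects per arm was selected as the minimum size to provide adequate power for the dose-proportionality assessment, our primary objective".

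**The concern.** A normal distribution with a CV of 35% or 45% yields some values at or below zero, and their logarithm does not exist. The protocol does not say what was done with them. The table shows a symptom: at CV 45% the stated power is 41.8, 43.5 and 43.6% for 8, 10 and 12 per arm. Enlarging each arm by half should not leave power almost unchanged.

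The linear column has a different fault. Its data are generated under exact proportionality, so the share of non-significant tests is a non-rejection rate under the null hypothesis. It says nothing about the ability to detect a departure from proportionality.

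Table 7-1 is the stated basis for 8 per arm as the minimum for the primary objective. As printed, it says that more participants gain almost nothing near the cited CV of 46%, and that 6 per arm is already enough under one approach. Neither statement comes from the design.

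**Working it through.** **Inputs.** Means 14 × (1, 2, 4, 7), SD = CV × mean, CVs and sample sizes from 7.3 and Table 7-1. Slope limits are 1 ± ln(2)/ln(7) = 0.644 and 1.356. Monte Carlo with 40,000 replicates per cell, using the 90% t-interval for the slope. The protocol's own 1000 replicates carry a standard error of about 1.2 points at 81% and 1.6 points at 42%.

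**How often a draw is at or below zero.** For one draw the probability is Φ(−1/CV): 0.00003, 0.0021 and 0.0131 at CV 25, 35 and 45%. For a whole replicate it is 1 − (1 − p)^(4n):
- CV 25%, n = 8: 0.1%
- CV 35%, n = 8: 6.6%
- CV 45%: 34.5% (n = 8), 41.1% (n = 10), 47.0% (n = 12)

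**Reproducing the column.** Scoring a replicate with any value ≤ 0 as a failure gives, at CV 25/35/45%:

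| n per arm | Stated | Reproduced |
|---|---|---|
| 6 | 98.4 / 74.9 / 33.3 | 98.5 / 73.5 / 33.9 |
| 8 | 99.7 / 81.1 / 41.8 | 99.6 / 82.1 / 40.4 |
| 10 | 99.8 / 85.0 / 43.5 | 99.8 / 85.4 / 42.6 |
| 12 | 99.7 / 85.2 / 43.6 | 99.8 / 86.6 / 42.6 |

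Flooring such values at 0.01 gives the same picture. Dropping only the offending values does not: 87.4/60.6% at n = 8, CV 35/45%.

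**Strictly positive data, same means 1:2:4:7.** Lognormal log-SD is √ln(1 + CV²). A normal cut at zero has a smaller CV than its nominal value (34.6% for 35%, 42.6% for 45%), so its parameters are reset to give an actual CV of 35% or 45%.

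| n, CV | Stated | Lognormal | Gamma | Truncated normal, actual CV |
|---|---|---|---|---|
| 6, 35% | 74.9 | 95 | 92 | 76 |
| 8, 35% | 81.1 | 99 | 98 | 87 |
| 8, 45% | 41.8 | 91 | 83 | about 53 |
| 12, 35% | 85.2 | 100 | 100 | 96 |
| 12, 45% | 43.6 | 99 | 96 | 74 |

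At CV 25% all three give 98.5 to 100%, so those cells barely move. At CV 45%, power from n = 8 to n = 12 rises in every column instead of stalling. With the nominal CVs the truncated normal would give 88/62% at n = 8, but those figures belong to actual CVs of 34.6/42.6%.

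**Linear column.** With exact proportionality, non-rejection is 93.6 to 94.7% over n = 6, 8, 12 and all three CVs (stated 93.2 to 96.1%), whatever the sample size or noise. With a true exponent of 0.5, Arm 4 has 7^0.5/7 = 38% of its proportional exposure. Non-rejection at n = 8 is then 32/62/77% at CV 25/35/45%, and at CV 35% it is 72/62/45% for n = 6/8/12. The measure improves with noise and worsens with sample size, the reverse of power.

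**Dependence on the means.** Section 1.2.2 gives 1:2:4:7 as anticipated exposures, while 7.6.1.1 tests Day 35 pre-dose concentrations. Assume first-order decline, the half-lives of 1.2.3 (k = ln 2/half-life) and last doses on Days 28, 31, 31 and 34, inferred from Table 5-3 and Figure 1-1. Relative troughs are then:
- Arm 1: e^(−168k)/(1 − e^(−168k))
- Arm 2: (e^(−168k) + e^(−96k))/(1 − e^(−168k)); Arm 3 is twice this
- Arm 4: e^(−24k)/(1 − e^(−24k))

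For TFV-DP (150 h) these are 0.852, 2.04, 4.08 and 8.53, or 1:2.4:4.8:10.0, with a fitted slope of 1.16. Power at n = 8 and CV 35% is 74% (lognormal), 70% (gamma) and 59% (truncated normal at nominal CV; 58% at actual CV). For FTC-TP (36 h) the ratios are 1:5.0:10.0:41.5, slope 1.81, and power is about 0.

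**The case against.** Several objections carry weight.

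- The handling of values ≤ 0 is inferred and not unique: failing the replicate and flooring at a tiny value fit equally well. This stands. The missing rule and the stall are nevertheless in the protocol itself.
- The error is on the safe side. For means of 1:2:4:7 this is true under all three positive distributions.
- The size of the error at CV 45% depends on an assumed shape, and lognormal is the most favourable. This stands. Under the least favourable shape tried, at an actual CV of 45%, the gap is about 11 points (53 against 41.8), and at CV 35% about 6.
- CV 45% is not the design case, because 7.3 argues for 25 to 35%. This is fair, although 7.3 also cites 46% and higher values.
- The linear column does not drive the choice of 8: the text rests that on the power model plus cost and operations, and 7.6.1.1 uses only the power model. That limits the consequence but does not make the sufficient-power sentence correct.
- The trough calculation rests on inferred dosing days. Section 2.3.2 speaks of synchronising the time since dose at 7 days across regimens. If every arm were sampled 7 days after its last dose, TFV-DP ratios would be about 1:1.7:3.4:5.1 (slope 0.86), not 1:2.4:4.8:10.0. The result is also sensitive to the half-life: 100 to 200 h gives 33 to 88% (lognormal, CV 35%, n = 8).

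A reader might infer that the whole power-model column is wrong. It is not: the CV 25% cells hold.

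**Conclusion.** Both faults are real. The CV 35% and 45% cells of the power-model column understate power for means of 1:2:4:7. With 8 per arm, positive data give 87 to 99% where 81.1% is printed, and about 53 to 91% where 41.8% is printed, depending on the distribution assumed. The near absence of gain beyond 8 per arm at CV 45% comes from non-positive draws. The linear column is a non-rejection rate of about 1 − alpha and supports no statement about power.

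Two stronger readings should be resisted. One is that, since at least 81% is conservative, 8 per arm is shown to be adequate. That holds only for means of 1:2:4:7 and CV up to 35%, and those ratios are exposures, not pre-dose concentrations. The other is that 8 per arm is shown to be inadequate. The figures of about 59 to 74% for TFV-DP and about 0 for FTC-TP at CV 35% rest on first-order decline and inferred dosing days, and the protocol's own passages on sampling time must first be reconciled. What the document supports is that adequacy for the Day 35 pre-dose endpoint is not shown. Nor does it show that 8 is a minimum: at CV 35%, 6 per arm gives 95, 92 or 76% for 1:2:4:7, depending on the distribution.

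**What to change.** 1. Confirm the Day 35 pre-dose mean ratios for TFV-DP and FTC-TP used in step 1, and reconcile them with the dosing days and with the 7-day post-dose statement in 2.3.2. Every power figure depends on this.
2. Re-run the power-model column with a strictly positive distribution: lognormal, stated as an assumption, with gamma and a truncated normal at the true CV as sensitivity analyses. Replace the CV 35% and 45% cells.
3. Make the 8-per-arm sentence conditional on mean ratios, distribution and CV. If 1:2:4:7 is confirmed, it could read: *With true Day 35 pre-dose means in the ratio 1:2:4:7, power with 8 per arm at CV 35% and 45% is about 99% and 91% for lognormal concentrations (assumed), 98% and 83% for gamma, and 87% and 53% for a normal truncated at 0.* Otherwise give the figures for the confirmed ratios. Drop the minimum-size wording or tie it to the same conditions.
4. Delete the linear column, or relabel it *probability of non-rejection under exact proportionality (about 1 − alpha), not power*. Delete the sentence calling 6 or 12 per arm sufficient.

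The cost is one check of the ratios, one short re-run, one table and a few sentences. This correction does not change enrolment, endpoints or the decision rule of 7.6.1.1.

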### **1.1.5 Drug Concentration Simulation Models**

In computer simulation models, the “expected” drug concentration is based on the PK characteristics of the drug and the prescribed dosing regimen of the study. To facilitate these simulations, PK data are available from several reports in which TDF (Viread®) has been administered to human research participants. From these studies, one can make some estimates of the effective intracellular half-life for tenofovir diphosphate (TFV-DP), the active moiety of the drug, which appears to be approximately ~150 hours (Hawkins et al., 2005; Pruvost et al., 2005; Pruvost et al., 2009). From these studies, however, the inter-individual variability for half-life and peak concentration ( $C_{max}$ ) for TFV-DP is relatively large (coefficient of variation around 50% to 65%). Accordingly, the best parameter estimates for such a simulation come from

individual study participants. To avoid intensive, frequent PK sampling, which would be cumbersome in a large clinical trial, one can employ a combination of (1) population-based estimates from the studies like those cited above, and (2) data from a few samples from each individual in a prospective study. To remove variability in adherence in estimation of individual PK parameter estimates, samples collected from the individuals tested should follow an observed dose, thus insuring 100% adherence without variability. With an observed dose, the possibility of variable adherence affecting subsequent drug concentrations is removed. This leaves the following variables to consider: inter-individual PK variability, assay variability, and unknown sources of noise that may vary with time in the environment. Examples of simulations of proposed dosing strategies of TFV-DP in PBMCs (Figure 1-1) and TFV in blood serum (Figure 1-2) are shown below.

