### **1.2.2 Dosing Regimen Rationale**

We propose to study four different dosing regimens of Truvada® (tablets include 300 mg TDF and 200 mg FTC): one tablet daily, two tablets twice weekly, one tablet twice weekly, and one tablet weekly. To provide adequate data on dose-proportionality, these regimens are selected to cover the range of concentrations achieved between daily and weekly dosing, representing a 7-fold range of anticipated drug concentrations. These regimens will achieve drug concentrations anticipated in current PrEP studies that employ daily dosing, as well as drug concentrations likely to be achieved with proposed intermittent PrEP regimens with dosing as infrequent as weekly or twice weekly dosing. In addition to studying three different dosing frequencies (daily, twice weekly, and weekly), we will study two different doses given twice weekly: a twice-weekly regular dose (one Truvada® tablet), and a twice-weekly double-dose (two Truvada® tablets). This will provide data on dose-proportionality for regimens between the weekly and daily dosing. Using the weekly one Truvada® tablet as reference, these four dosing regimens represent anticipated drug exposures of 1x (weekly), 2x (twice weekly), 4x (double-dose twice weekly), and 7x (daily). These proportions will provide sufficiently rich data to assess dose-proportionality. If dose-proportionality is determined not to hold between weekly and daily dosing, the middle dose regimens provide intermediate points to increase the accuracy with which we can determine the point of deviation from dose-proportionality. Further, they will provide rich drug concentration data to understand these intermediate dosing regimens, which may prove useful in future PrEP efficacy studies should the concentrations of drug prove insufficiently low with weekly dosing.

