## **7.6 Data Analysis**

### **7.6.1 Primary Analyses**

#### **7.6.1.1 Dose Proportionality**

Dose proportionality will be assessed by a confidence interval approach based on the power model, using Day 35 pre-dose concentration ( $C_t$ ) data from all evaluable participants in Arms 1-4. Dose-proportionality will be declared if the 90% confidence interval of the slope completely falls in the critical interval ( $1 + \frac{\ln(0.5)}{\ln(7)} = 0.64, 1 + \frac{\ln(2)}{\ln(7)} = 1.36$ ). Analyte concentrations assessed for dose-proportionality will include TFV and FTC in fluids and their phosphorylated moieties, TFV-DP and FTC-TP, in cells. TFV-DP and FTC-TP will also be assessed in tissue homogenates. Weight-based or creatinine clearance-adjusted intracellular PK parameters may also be used in evaluating dose-proportionality (as well as secondary outcomes). Biological matrices included in the analysis will include: serum, PBMC, CD4+ blood cells, rectosigmoid and vaginal luminal fluid, semen, and rectosigmoid and vaginal tissue specimens (total tissue cells, CD4+ tissue cells, tissue homogenate) (see Table 7-3).

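### The planning CV of 25-35% is optimistic against most of the protocol's own TFV-DP figures, and the power values in Table 7-1 are distorted by logging normal data

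*Protocol*

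**What the plan says.** Section 7.6.1.1 sets the primary rule: "Dose-proportionality will be declared if the 90% confidence interval of the slope completely falls in the critical interval", with limits 0.64 and 1.36. Section 7.3 sizes the trial for that rule by simulation. Its first step is "Generate random samples of size n from a normal distribution" with mean 14 × dose and SD equal to CV × mean, at relative doses 1, 2, 4 and 7. Concentrations are then logged and regressed on log dose. On numbers, "An equal number of participants (8 per arm) will be randomized into each of the four dosing arms".

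For the CV, Section 7.3 reports TFV-DP values of 46% (an HIV prevention study), 28, 36, 35 and 54% (a drug interaction study), and 42% and 83% (two groups of a 2005 study). It also uses a seven-subject study that gives only a range of median concentrations, 85-110: "Imputing values from the extremes of this range would yield a CV of approximately 14" per cent. It then notes that none of these studies dosed a single drug under observation in healthy volunteers, and concludes "Given that the DOT used in this study is likely to reduce the variability, a CV estimate of 25-35% seems to be realistic".

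Table 7-1 gives the confidence-interval approach with 8 per arm 99.7%, 81.1% and 41.8% power at CVs of 25, 35 and 45%. The text below it calls a CV of 35% or less "a reasonable degree of variation given the argument above" and makes this a reason for choosing 8 per arm.

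**The concern.** The top of the planning range lies below the centre of the values listed to support it. The one argument for going lower, observed dosing, comes with no amount. Section 1.1.5 also says that after an observed dose, between-person pharmacokinetic variability, assay variability and other noise remain. The lowest cited value, 14%, is not a between-person CV at all.

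At stake is what the protocol tells its readers about the primary objective. The power statement is tied to the favourable part of the evidence, and the simulated grid stops at 45%, short of the cited 46, 54 and 83%. Power in the table also falls from 81% to 42% between CVs of 35 and 45%, which is steep enough to ask whether the simulation itself is sound. If a proportionality result fails, readers need to know at what variability 8 per arm stops being enough.

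**Working it through.** **1. The CV evidence.** The reported between-person values in order are 28, 35, 36, 42, 46, 54, 83. The median is 42%, and five of seven exceed 35%. With the 14% added, five of eight exceed 35% and the median is (36 + 42)/2 = 39%. The 14% can be rebuilt by placing four subjects at 85 and three at 110: mean 95.7, SD 13.4, ratio 14.0%. That placement is my assumption, but it shows the figure is a construction from two end points.

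**2. Reproducing Table 7-1.** Inputs from Sections 7.3 and 7.6.1.1: 8 per arm, doses 1, 2, 4, 7, y ~ N(14 × dose, CV × mean), least-squares slope of log y on log dose, and a 90% t-interval inside (0.644, 1.356). A normal draw can be zero or negative and then has no logarithm. If any replicate containing such a draw counts as a failure, power is 99.6%, 82% and 40% at CVs of 25, 35 and 45%, against the printed 99.7%, 81.1% and 41.8%. With that convention all twelve confidence-interval cells agree within 2 points. Dropping those replicates instead gives about 87% at CV 35% and 61% at 45%, which does not match.

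**3. How often this happens.** The chance that one draw is non-positive is Φ(−1/CV), and there are 32 draws per replicate.
- CV 35%: Φ(−2.857) = 0.00214, so 1 − (1 − 0.00214)^32 = 6.6%.
- CV 45%: Φ(−2.222) = 0.01313, so 1 − (1 − 0.01313)^32 = 34.5%.

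At CV 45% the table therefore cannot exceed 65.5% with 8 per arm. With 12 per arm (48 draws) the ceiling is 0.98687^48 = 53%. This explains why the printed power at CV 45% barely moves (41.8, 43.5 and 43.6% for 8, 10 and 12 per arm). Small positive draws distort the log scale further.

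**4. Log-normal data.** I assume true slope 1 and SD of log y of σ = √ln(1 + CV²). The squared deviations of log dose sum to 2.138 across the four doses, or 17.10 with 8 per arm, so SE = σ/√17.10. With t(0.95, 30 df) = 1.697 and margin 0.3562, power is approximately 2Φ[(0.3562 − 1.697 SE)/SE] − 1. At CV 42%, σ = 0.403, SE = 0.0975 and power ≈ 2Φ(1.96) − 1 = 95%. At CV 52%, SE = 0.1183 and power ≈ 2Φ(1.31) − 1 = 81%. Simulation agrees:

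| CV | Protocol's model, non-positive = failure | Log-normal |
|---|---|---|
| 35% | 82% | 99% |
| 42% | 53% | 95% |
| 45% | 40% | 91% |
| 46% | 36% | 90% |
| 52% | 19% | 80% |
| 54% | 15% | 77% |
| 65% | 4% | 56% |
| 83% | 0.3% | 27% |

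**The case against.** The protocol does not hide the problem. It says the source CVs vary widely, lists all of them including 83%, labels the 14% as imputed, prints the 45% row and warns that power for the confidence-interval approach depends heavily on the CV. Two of the seven values lie inside the planning range. Beyond observed dosing, the design limits age to 18-44 to reduce variability, requires creatinine clearance of at least 70 mL/min, fixes blood draws to the hour before dosing and excludes drugs that compete for renal secretion. All of this stands, and it makes 25-35% an optimistic but disclosed judgement. It does not supply the size of the reduction that the judgement needs.

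A reader might go further and infer that the protocol contradicts itself, because Section 1.1.5 puts TFV-DP variability at 50-65%. That does not follow. The 50-65% describes half-life and peak, while the primary analysis uses the Day 35 pre-dose concentration. It also cites the same published studies as Section 7.3, so it is context and not independent evidence.

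A reader might also infer from Table 7-1 that the trial has only about 42% power once the CV reaches 45%, and is too small. The documents do not support that either. The 41.8% is largely a product of the generating model. On the log-normal scale, power at the centre of the cited values (90-95%) exceeds the 81% claimed.

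**Conclusion.** The point holds in two parts. First, the 25-35% planning CV is optimistic against most of the protocol's own figures and rests on an unquantified effect of observed dosing. Second, the confidence-interval column of Table 7-1 is distorted because normal data are logged, so neither 81.1% nor 41.8% is a sound statement of power at its CV.

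The two errors pull in opposite directions. Corrected together, 8 per arm is adequate at the centre of the evidence (95% at CV 42%, 90% at 46%) and keeps 80% power up to a CV of about 52%. It does not cover the full cited range: 77% at 54% and 27% at 83%. This is a fault in the justification and the printed numbers, not in the sample size.

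The result assumes log-normal concentrations, which the protocol does not state, a true slope of 1 and an equal CV in all arms. All the cited CVs are for TFV-DP. None is given for FTC-TP, which shares the primary objective.

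**What to change.** In Section 7.3:

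- Rerun the power-model confidence-interval simulation with log-normal data and state that assumption.
- Remove the 14% from the CV justification.
- Plan at about 42-46%, the centre of the reported values, unless a figure for the effect of observed dosing can be given.
- Replace the confidence-interval column of Table 7-1 with power for 8 per arm over the cited CVs: about 99% at 35%, 95% at 42%, 90% at 46%, 80% at 52%, 77% at 54%, 56% at 65% and 27% at 83%.
- Say plainly that 8 per arm keeps 80% power up to a CV of about 52% and not beyond.

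The cost is one simulation and a reworded paragraph. The number of participants, the design and the primary analysis rule stay as they are.
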